1.3 Preclinical Data

N/A

1.4 Clinical Data to Date

Hormone Challenge Protocol. [name] team at the NIH previously employed the proposed protocol to examine reproductive-related affective dysfunction in 16 women (Bloch et al., 2000). Women with a history of postpartum depression showed significant increases in depressive symptoms during both hormone addback and withdrawal compared with baseline, whereas the control group did not (Bloch et al., 2000). To our knowledge, this was the first direct evidence to support the involvement of ovarian hormones in the development of PND in a subgroup of susceptible women. We replicated this finding in a larger group of women (N=30; 15 with a history of PND and 15 controls without such a history) and included both fMRI and more comprehensive depression and anxiety assessments, which revealed that the mood changes in HS+ are primarily driven by increased irritability.

Recruitment and Retention. Our successful completion of the previous study (N=30) involving the proposed hormone challenge and neuroimaging demonstrates both the feasibility of the proposed protocol and our ability to recruit and retain participants. Participants were recruited primarily via social media (57%) and other online recruitment tools (30%). Of those who began the hormone protocol, only 3 women (9%) dropped out: one who experienced a traumatic life event and consequent psychiatric symptoms unrelated to the study, and two because of logistical problems involved with attending biweekly study visits at UNC Hospital. Consequent to these dropouts, we modified the protocol to conduct all biweekly study visits in participants' homes, which subsequently improved retention. We have estimated an equivalent attrition rate in the current study despite the truncated protocol and the provision of home visits for all but the OBGYN and fMRI sessions, which will likely reduce attrition. Of note, none of the women in this or any of [name] previous studies employing hormone challenge protocols experienced serious adverse events.

Use of the Hormone Challenge Protocol to Provoke Irritability and Dysregulate Striatum in HS+.

Women with a history of PND reported increased irritability, anxiety, dysphoria, and anhedonia during the hormone challenge. Eleven out of 15 (73%) women with a history of PND were HS+ (i.e., showed a 30% increase in IDAS-II affective symptoms during early addback, late addback, or withdrawal compared with baseline). Irritability was the primary symptom for the majority (72%) of HS+, and because irritability distinguished HS+ and HS- as early as 2 weeks into hormone addback ($t=2.97$, $p<.004$; Figure 4), we propose to truncate hormone addback in the current study to 2 weeks (down from 8 weeks in the previous study) and conduct the second fMRI at that time. During the monetary incentive delay (MID) task, there was a significant group x time interaction in the bilateral putamen ($F=5.9$,

$p < .022$), such that HS- showed greater activation than HS+ during hormone withdrawal ($t(26) = 2.8$, $p < .01$) but not at baseline ($t(26) = -0.6$, $p = .54$) (see Figure 5).

[figure not shown]

Figure 4. Irritability self-ratings during each study phase. HS+ ($n=11$) showed significantly increased irritability at early addback, compared with baseline and compared with HS- ($n=14$). The early addback assessment occurred 2 after two weeks of hormone addback (plus Lupron). Symbols:  fMRI session.

[figure not shown]

Figure 5. Percent signal change in bilateral putamen activity during monetary reward at baseline and during hormone withdrawal. Consistent with the literature, as HS+ ($n=11$) became depressed, they showed reduced striatal activation to reward, compared with HS- ($n=14$; non-depressed).

1.5 Dose Rationale and Risks/Benefits

Dose Rationale

The rationale for the dose of each drug administered in the proposed study is based on the study referenced immediate above. As shown in Figure 4, we found a statistically significant difference in irritability between HS+ and HS- after only 2 weeks of hormone addback, whereas we had administered hormones for a total of 8 weeks in the previous study. Moreover, the first two weeks of hormone addback involved doses (2 mg E2 bid and 200 mg P4 bid), which were half that given in the last 6 weeks of hormone addback. Based on these data, our proposed hormone addback protocol will include 2 mg E2 bid and 200 mg P4 bid for a period of 2 weeks. This shorted addback period will further allow us to reduce the number of Lupron injections from 4 in the previous protocol to 2 in the current protocol. Thus the drug protocol, including the route of administration, dosage, dosage regimen, and dosage period, mirrors a truncated version of our previous study which included a 7-month-long hormone manipulation protocol that included higher dose hormones and a previous study conducted at the NIH, which both successfully modeled the hormonal events of pregnancy and parturition and precipitated the onset of mood symptoms in susceptible women (Bloch et al., 2000, 2005).

Risks/Benefits

We do not expect any adverse side effects associated with the hormonal manipulations outlined in this protocol for the following reasons: First, we will be administering the physiologically relevant steroid hormones (estradiol and progesterone) and not the substituted steroids (such as ethinyl estradiol or norethindrone) present in many oral contraceptives and which have been reported to have a potentially more serious profile of side effects. Second, the doses of Lupron, estradiol and progesterone, and the duration for which they will be administered in this protocol, will result in plasma hormone levels comparable to those commonly used for in vitro fertilization (IVF) protocols lasting 1-3 months. Therefore, based on current IVF procedures we do not anticipate any adverse incidents arising from the proposed doses of estradiol and progesterone (Chetkowski et al., 1986; Rice et al., 1993; Saleh et al., 1995). Third, no adverse reactions or events were encountered in past studies conducted with this protocol in [name] lab at the NIH. Finally, comparable extended, uninterrupted gonadal steroid treatment (such as oral contraceptives) for 6 to 12 weeks has been shown to be well-tolerated (Sulak et al., 1997).

Lupron: The most frequent adverse effect of Lupron is hot flushes (flashes) reportedly occurring in 4-89% of patients receiving the drug. Lupron-induced hot flushes have ranged in severity from occasional mild flushing to frequent sweating. Episodes of flushing appear to decrease with continued therapy in most patients receiving Lupron; however, in at least one study, the incidence of hot flushes did not appear to decrease with continued therapy. In a recently completed study of 400 women of reproductive age with either uterine fibroids or endometriosis who each received 3.75 mgs depot Lupron every month for a period of six months, the most common side effects reported to occur were as follows: 1) hot flashes of mild to moderate intensity (89%), 2) headache (22%), 3) nervousness or irritability (11%), and 4) insomnia (10%). Local irritation at the injection site was complained of in less than 10% of the patients in this sample, and there was a mean decrease in bone density, as measured by bone densitometry, of 3.4 to 4.0%, which totally reversed after the medication had been discontinued for six months. Approximately ten patients of the original sample of 400 found the side effects to be severe enough to discontinue therapy. In the majority of women regular menstrual cycle function returned within two months following the last injection of depot Lupron (Tapp Pharmaceuticals, personal communication). Blurred vision, myalgias, lethargy, memory disorder, and numbness have been reported in less than 3% of patients receiving the drug. Thrombophlebitis, pulmonary embolus, and congestive heart failure have occurred rarely in patients receiving Lupron, but a causal relationship to the drug has not been established. Adverse GI effects occurring in 2% or more of patients receiving Lupron include nausea and/or vomiting, constipation, and anorexia. Diarrhea and a sour or unusual taste in the mouth have been reported less frequently. Other adverse effects of Lupron occurring in less than 3% of patients include decreased hematocrit and hemoglobin concentration, fatigue, fever, facial swelling, rash, hives, hair loss, and itching. From our experiences with a longer protocol using the same medications in 15 women with a history of PPD and 15 controls, Lupron is well tolerated (no dropouts) with the most common side effect being hot flushes. Limited information is available on the acute toxicity of Lupron. Following subcutaneous administration of Lupron in rats at dosages 250-500 times the usual human dosage, dyspnea, decreased activity, and local irritation at the injection site were observed; however, there is no evidence to date that overdosage in humans produces similar adverse effects. Lupron dosages up to 20 mg daily for up to two years have not produced unusual adverse effects in humans. There has been one report of an anaphylactic reaction in a patient following administration of a GnRH agonist. Recent longitudinal follow-up studies of girls and boys

receiving GnRH agonists as a treatment for precocious puberty report the development of normal reproductive function, skeletal growth, and fertility (Feuillan et al., 1999, 2000).

Estradiol: Nausea is the most common side effect of estrogen administration. At conventional replacement doses, higher than those employed in this protocol, this complaint seldom interferes with eating, and no weight loss has been reported. Breast engorgement, endometrial hyperplasia and bleeding are also common side effects of estrogen administration. Pre-existing fibroid tumors of the uterus may enlarge under the effects of estrogen; however, at the dosage and for the duration of estrogen administration in this protocol this risk is small.

The relationship between estrogen, both endogenous and exogenous, and the development of endometrial carcinoma has been suggested by several different lines of investigation (Gambrell, 1986). Numerous retrospective case control studies published since 1975 have indicated that post-menopausal exposure to unopposed estrogens for more than one year results in a two to 12 fold increased relative risk for endometrial cancer. A relationship between the dose and duration of estrogen use and the risk for endometrial cancer has also been shown, the risk being increased after one to four years of estrogen use and rising also with the dosage employed. However, the addition of progesterone to estrogen replacement therapy appears to decrease the risk of endometrial hyperplasia and endometrial cancer to equal or below that of women receiving no hormonal treatment. Recent studies suggest that the optimal regimen to prevent hyperplasia during long term ERT and thus, inferentially, the risk of carcinoma, consists of 12 to 13 days of progesterone treatment each month when estrogens are administered (Nieman & Loriaux, 1992). There is an increase in thromboembolism in women receiving non-contraceptive estrogen therapy (Cushman et al., 2004; Daly et al., 2001; F. Grodstein et al., 1996; Jick et al., 1996). Additionally, some but not all studies report an increase in risk of stroke (Stampfer et al., 1991; Wassertheil-Smoller et al., 2003) in older women taking estrogen therapy. However, these complications are unlikely at the dose and duration of estrogen replacement employed in this protocol, and in the younger age group of women who participate in this study. One study (Chetkowski et al., 1986) reported no effect of the estrogen patch on the four clotting indices previously shown to be altered by oral contraceptive use (Mandel et al., 1983; Melis et al., 1984; Nieman & Loriaux, 1992). Blood pressure, on average, appears to be unaffected by estrogen therapy, although both increases and decreases have been reported. In observational studies, post-menopausal estrogen therapy has been observed to lower the relative risk of cardiovascular disease in some but not all studies (Barrett-Connor & Bush, 1991; Stampfer et al., 1991). In contrast, recent randomized controlled trials in older postmenopausal women (e.g., Women's Health Initiative [WHI]) report an increased risk of cardiovascular disease (Manson et al., 2003). Emerging data suggest that these disparities in findings may be related to the timing of initiation of estrogen therapy in relation to the proximity of menopause. Subgroup analyses of the combined estrogen and progestin (EPT) arm of the WHI demonstrated a significant interaction between coronary heart disease (CHD) risk and time since initiation of EPT, with an increased risk in the early years following initiation and a decreased risk in later years. Additionally, the increased risk of CHD was observed in older but not younger perimenopausal women (Francine Grodstein et al., 2006; Hsia et al., 2006; Lobo, 2004; Manson et al., 2003; Prentice et al., 2005, 2006). High doses of oral estrogens have been reported to elevate hepatocellular enzyme levels and, less commonly, cause cholestatic jaundice. The risk for gallstones and hepatocellular adenomas has been reported to be increased in association with oral contraceptive

use, and although uncommon these complications may also occur with the use of replacement doses of estrogen (Cirillo et al., 2005; Petitti et al., 1988). Estrogen therapy also may increase the risk of urinary incontinence in older postmenopausal women (F. Grodstein et al., 2004; Hendrix et al., 2005; Steinauer et al., 2005). Further, most studies have suggested an increased relative risk of breast cancer after four or five years' use(Beral, 1997; Chen et al., 2006; Chlebowski et al., 2003; Colditz et al., 1995; Gann & Morrow, 2003; Grady & Ernster, 1991; Li et al., 2003; Rossouw et al., 2002; Stefanick et al., 2006; Sturmer & Manson, 2004; Wingo et al., 1987), similar to the risk expected if the onset of menopause was delayed for a comparable length of time. Due to the publicity surrounding the cancellation of the treatment arm of the Women's Health Initiative study (Rossouw et al., 2002) that involved the administration of combined conjugated estrogens and medroxyprogesterone acetate (Prempro), we have included the following statement in the consent documents:

Adverse Events Related to Combined Hormone Replacement and the Results of the Women's Health Initiative (WHI): The WHI study demonstrated that continuous administration of one form of estrogen (conjugated estrogens) in combination with one form of progesterone (medroxyprogesterone acetate) is associated with an increased risk of dementia, heart attacks, stroke, blood clots, and breast cancer. Estradiol, the form of estrogen that we use in this study, is administered as a sole agent (with the exception of one week's combination with progesterone) and, consequently, we do not expect that it will pose the increased risks observed with the chronic combination of the conjugated estrogens and medroxyprogesterone administered in the WHI study. Indeed, while the estrogen alone arm of the WHI trial was shown to be associated with an increased risk of stroke, no increased risk of either heart disease or breast cancer was observed (Anderson et al., 2004; Rossouw et al., 2002). Estrogens may precipitate migraine headaches, and depression has also been reported to occur with the use of estrogens. In general, considering the dose and duration of treatment that we propose to use in this protocol, the risk of developing such side effects is negligible.

Progesterone: Progesterone and the synthetic progestins are widely prescribed, with indications including dysfunctional uterine bleeding, endometriosis, mastodynia, galactorrhea, and precocious puberty (Henzel, 1986). Side effects reported in women taking progestins may include breakthrough bleeding, edema, change in weight (increase or decrease), cholestatic jaundice, rash (with or without pruritus), depression, easy fatigue and sedation, lack of initiative, and chloasma. Since progestins are often used in women with antecedent menstrual irregularity, it is not clear whether the breakthrough bleeding represents an effect of the medication or refractoriness to treatment. In the large majority of patients, menstruation occurs predictably following withdrawal of progestins and is usually more regular than in spontaneous cycles. In a recent study, an average dose of 1750 mg of oral micronized progesterone was given to 59 women with PMS for a period of three months and was well tolerated by this sample. The side effects reported on progesterone were lightheadedness, fatigue, forgetfulness, and headaches. These were very mild and caused no dropouts.

For the sake of completeness, we will also describe the side effects reported when estradiol and progesterone are combined in the form of oral contraceptives. Side effects observed in patients receiving combined oral contraceptives include nausea, breast soreness, vaginal discharge, fluid retention, hypertension, and clotting abnormalities that have been associated with the estradiol component of the oral contraceptive. Thromboembolic disorders including thrombophlebitis, pulmonary

embolism, and cerebral and coronary thrombosis appear to occur with greater frequency in women taking oral contraceptives. While the increased incidence of these disorders has been associated with the estradiol component of the oral contraceptives, it is now believed that the progestogen component may, to a lesser extent, contribute to the increased risk. There are relatively few reports associating oral contraceptives with the development of carcinomas (vaginal, uterine, hepatic, and mammary) despite the vast use of these agents, although this may reflect the latent period needed for cellular transformation. Finally, several reports suggest an association between intrauterine exposure to female sex hormones and congenital anomalies.

Lupron, Estradiol, and Progesterone Combined Administration: As discussed in Section 1.2, the proposed monthly 3.75-mg injection of leuprolide acetate (Lupron Depot) is FDA-approved for use in premenopausal women to treat endometriosis and uterine fibroids. Lupron has also been widely researched in healthy premenopausal women (Flory et al., 2002; Grigorova et al., 2006; Matthews et al., 1998; Sánchez et al., 2002) and to treat a variety of conditions, including ovarian epithelial tumor cells (Thompson et al., 1991), insulin resistance (Elkind-Hirsch et al., 1993), endometrial stromal sarcoma (Scribner Jr. & Walker, 1998), and infertility (Padilla et al., 1991). Several studies have investigated the use of Lupron and hormone addback to treat the symptoms of premenstrual syndrome and premenstrual dysphoric disorder (Lee et al., 2012; Mitwally et al., 2002; Wyatt et al., 2004), which has resulted in combined Lupron and estrogen/progestin supplementation as a recommended long-term treatment for premenstrual syndrome (Kaur et al., 2004; Mezrow et al., 1994). Healthy women undergoing in vitro fertilization (IVF) routinely receive luteal supplementation of 600 mg progesterone daily along with 6 mg oral micronized estradiol (Lukaszuk et al., 2005) in combination with GnRH agonists (e.g., Lupron).

GnRH agonist treatment combined with hormone addback (i.e., high-dose estradiol and progesterone supplementation) has been previously studied in large randomized controlled trials for the purpose of IVF (Damario et al., 1999; Fatemi et al., 2006; Friedler et al., 1999; Humaidan et al., 2005; Lukaszuk et al., 2005). Of particular relevance to the current study, researchers induced a hypogonadal state using 3.75 mg Decapeptyl, followed by high-dose (800 mg) oral progesterone treatment in 32 women without an adverse event (Friedler et al., 1999). Several studies have examined the use of combined Lupron treatment (1 mg daily or 3.75 mg monthly), oral micronized estradiol (max doses ranged from 4 mg to 9 mg daily), and either oral (900 mg daily), vaginal (90-600 mg daily), or i.m. (50-200 mg daily) progesterone administration in over 1800 healthy women (Bourgain et al., 1990; Bustillo et al., 1995; Daly et al., 2001; Damario et al., 1999; Engmann et al., 2008; Friedler et al., 1999; Legro et al., 1993; F. Licciardi et al., 2001; F. L. Licciardi et al., 1999; Mirkin et al., 2003; Nagy et al., 2009; Noyes et al., 2001; Paulson et al., 1997; Peress & Philips, 1998; Roca et al., 2003; Sauer et al., 1992; Tao & Tamis, 1997; Tonguc et al., 2011). Of note, Damario et al. (1999) reported the use of combined Lupron treatment, 9 mg oral micronized estradiol, and 100 mg i.m. progesterone in 238 healthy women presenting for IVF.

[name] team at the NIH has examined the combined administration of Lupron and estradiol/progesterone in healthy premenopausal women in several studies without a significant adverse event (Berman et al., 1997; Bloch et al., 2005; Daly et al., 2001; Roca et al., 2003; Schmidt et al., 2009). Moreover, the same drug protocol proposed in the current study has been employed

previously by our research team and [name] research team at the NIH (Bloch et al., 2000, 2005) and is currently being used in ongoing projects at the NIH under the direction of [name] and [name]. Thus, a large number of healthy women have previously received combined Lupron with high-dose oral estradiol and progesterone supplementation either as part of a research study or routine IVF treatment without significant side effects or adverse events.

The prior protocol most relevant to the current proposal is the trial we completed most recently, which used higher doses of hormones (at least twice the doses of both E2 and P4 proposed here) and for a longer duration (8 weeks versus 2 weeks) and was classified as IND exempt by the FDA. To clarify differences between the protocol described in our IND application and that proposed here, we have summarized the medication regimens in the table below.

Table 2. Medication Regimens in previous IND Exempt Protocol and the Proposed Protocol

	Past IND Exempt Protocol				Current Protocol		
Phase	1: Hypogonadism	2: Low Dose Addback	3: High Dose Addback	4: High Dose Withdrawal	1: Hypogonadism	2: Low Dose Addback	3: Low Dose Withdrawal
Duration	4 weeks	2 weeks	6 weeks	4 weeks	4 weeks	2 weeks	2 weeks
Lupron	3.75 mg IM dose #1	3.75 mg IM dose #2	3.75 mg IM dose #3	3.75 mg IM dose #4	3.75 mg IM dose #1	3.75 mg IM dose #2	N/A
Estrace	Placebo	2 mg bid	5 mg bid	Placebo	Placebo	2 mg bid	Placebo
Prometrium	Placebo	200 mg bid	400 mg bid	Placebo	Placebo	200 mg bid	Placebo

Below (Table 3) is a list of the adverse events that occurred in the previous, IND exempt protocol conducted at UNC using the same hormone protocol as that proposed in the current study. We have listed the adverse events that occurred during phases 1 and 2 (highlighted in yellow), which involved administration of medications, doses, and durations that are identical to those proposed in the current study, separately from those that occurred in phases 3 and 4 (highlighted in blue), which involved Estrace and Prometrium administration and withdrawal from doses that were at least twice those proposed in the current study and durations that were three times as long.

Table 3. Adverse Events in the Previous IND Exempt Protocol

	1: Hypogonadism	2: Low Dose Addback	3: High Dose Addback	4: High Dose Withdrawal	5: Follow-up	TOTAL
Cognitive:						
Drowsiness	1	1	4	1		7
Sedation		3	4			7
Dizziness	1	5	3			9
Lightheadedness		1	4			5
Memory impairment			1			1

Psychological:						
Depression		2	2			4
Anxiety		1				1
Irritability		2			1	3
Mood Swings		1	1			2
Trouble concentrating	1					1
Night Terrors		1				1
Gastrointestinal:						
Nausea		1	1			2
Diarrhea	1					1
Upset Stomach				1		1
Constipation	1				1	2
Heart Burn	1	1				2
Cardiac:						
Transient Heart Palpitations*	1					1
Chest Pain*		1	1			2
Arrhythmia*	1					1
Bradycardia*	1					1
Menstrual:						
Spotting	1		3			4
Prolonged menstrual bleeding			1	1		2

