Chemical name: 5-oxo-L-prolyl-L-histidyl-L-tryptophyl-L-seryl-L-tyrosyl-D-leucyl-L-leucyl-L-arginyl-N-ethyl-L-prolinamide

Progesterone

Active ingredient: micronized progesterone
Chemical name: pregn-4-ene-3, 20-dione

Dose:

Drug	Dosage	Formulation
Estradiol	2 mg bid	Oral capsule
Lupron Depot	3.75 mg/month	Intramuscular injection
Progesterone	200 mg bid	Oral capsule

Route:

Drug	Route of Administration
Estradiol	Oral
Lupron Depot	Intramuscular injection
Progesterone	Oral

Regimen:

Induced Hypogonadism. After the baseline period, participants will receive their first injection of the gonadotropin-releasing hormone (GnRH) agonist leuprolide acetate (Lupron) 3.75 mg/month via intramuscular injection, which is administered to produce a stable hypogonadal condition (after the initial “flair”). The first Lupron

	
injection will be administered on day six of the participants' first menstrual cycle after the baseline period and at monthly intervals thereafter until follow-up. During the month of GnRH agonist administration, all participants will receive placebo progesterone and placebo estradiol tablets and will be told that at some point the placebo pills will be switched to active medication.
 
Addback. After the fourth week of Lupron-alone treatment (i.e., hypogonadism), high plasma levels of estradiol and progesterone will be attained via micronized progesterone and estradiol tablets for two weeks (with continued Lupron administration). Estradiol will be administered at a dose of 2 mg bid (i.e., a total of 4 mg per day). Progesterone will be administered at a dose of 200 mg bid (i.e., a total of 400 mg per day). The blood levels that we expect to achieve and sustain in each woman will be approximately 500 pg/ml of estradiol and 30-40 ng/ml of progesterone.
 
Withdrawal. After two weeks of hormone replacement, active hormone tablets will be replaced with placebo tablets to induce a precipitous drop in plasma estradiol and progesterone levels. Lupron will maintain hypogonadal levels for the two-week withdrawal phase. The second fMRI session will take place at the beginning of the withdrawal period.

Duration of administration	8 weeks
Reference therapy	Placebo

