Induced Hypogonadism. After the baseline period, participants will receive their first injection of the gonadotropin-releasing hormone (GnRH) agonist leuprolide acetate (Lupron) 3.75 mg/month via i.m. injection, which is administered to produce a stable hypogonadal condition (after the initial “flair”). The first Lupron injection will be administered at the end of Study Visit 3 on day six of the participants’ first menstrual cycle after the screening period and again one month later. During the first month of GnRH agonist administration, all participants will receive placebo capsules (identical in appearance and number to the hormone capsules they will receive later) and will be told that at some point the placebo pills will be switched to active medication.

Addback. After one month of Lupron-alone treatment (i.e., hypogonadism), high plasma levels of estradiol and progesterone will be attained via micronized progesterone and estradiol tablets for two weeks (with continued Lupron administration). Participants will take 2 mg of estradiol twice daily (for a total of 4 mg/day) and 200 mg of progesterone twice daily (for a total of 400 mg/day). The second fMRI session will take place at the conclusion of the 2 weeks of hormone addback. Withdrawal. After 2 weeks of hormone addback, active hormone tablets will be replaced with placebo tablets to induce a precipitous drop in plasma estradiol and progesterone levels. Lupron will maintain hypogonadal levels for the 2-week withdrawal phase.

Follow-up. Participants will be followed for four more weeks while unmedicated. Based on our past experience, estradiol, progesterone, and mood symptoms are expected to return to baseline levels

in all participants by follow-up week 4. The withdrawal and follow-up phases, along with the addback phase, are used for the purpose of ensuring correct classification of subjects as HS+ and HS-.

Clinical Assessments

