
2005; Steinauer et al., 2005). Further, most studies have suggested an increased relative risk of breast cancer after four or five years' use(Beral, 1997; Chen et al., 2006; Chlebowski et al., 2003; Colditz et al., 1995; Gann & Morrow, 2003; Grady & Ernster, 1991; Li et al., 2003; Rossouw et al., 2002; Stefanick et al., 2006; Sturmer & Manson, 2004; Wingo et al., 1987), similar to the risk expected if the onset of menopause was delayed for a comparable length of time. Due to the publicity surrounding the cancellation of the treatment arm of the Women's Health Initiative study (Rossouw et al., 2002) that involved the administration of combined conjugated estrogens and medroxyprogesterone acetate (Prempro), we have included the following statement in the consent documents:

Adverse Events Related to Combined Hormone Replacement and the Results of the Women's Health Initiative (WHI): The WHI study demonstrated that continuous administration of one form of estrogen (conjugated estrogens) in combination with one form of progesterone (medroxyprogesterone acetate) is associated with an increased risk of dementia, heart attacks, stroke, blood clots, and breast cancer. Estradiol, the form of estrogen that we use in this study, is administered as a sole agent (with the exception of one week's combination with progesterone) and, consequently, we do not expect that it will pose the increased risks observed with the chronic combination of the conjugated estrogens and medroxyprogesterone administered in the WHI study. Indeed, while the estrogen alone arm of the WHI trial was shown to be associated with an increased risk of stroke, no increased risk of either heart disease or breast cancer was observed (Anderson et al., 2004; Rossouw et al., 2002). Estrogens may precipitate migraine headaches, and depression has also been reported to occur with the use of estrogens. In general, considering the dose and duration of treatment that we propose to use in this protocol, the risk of developing such side effects is negligible.

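### The WHI risk statement calls estradiol a sole agent apart from one week with progesterone, but the regimen gives both hormones together for the full two-week addback and never estradiol alone

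*Combined protocol and SAP*

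**What the plan says.** The WHI statement closes the estradiol risk text in Section 1.5 (Dose Rationale and Risks/Benefits). The protocol introduces it with "we have included the following statement in the consent documents". It lists the harms that WHI found with continuous conjugated estrogens plus medroxyprogesterone. It then says that this study's estradiol "is administered as a sole agent (with the exception of one week's combination with progesterone) and, consequently, we do not expect" those increased risks. The next sentence turns to the WHI trial of estrogen without a progestin: "while the estrogen alone arm of the WHI trial was shown to be associated with an increased risk of stroke", it reports no increase in heart disease or breast cancer. Appendix C (Data and Safety Monitoring Plan, Section II.A) carries the same statement, again saying that estradiol "is administered as a sole agent (with the exception of one week's combination with progesterone".

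The regimen is described differently. The Study Summary and Section 5.2 both say that the high addback hormone levels are reached "via micronized progesterone and estradiol tablets for two weeks (with continued Lupron administration". Section 6 gives the doses: "Participants will take 2 mg of estradiol twice daily (for a total of 4 mg/day) and 200 mg of progesterone twice daily", the latter totalling 400 mg/day.

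**The concern.** The statement asserts two facts: that estradiol is mostly taken alone, and that the overlap with progesterone lasts one week. Neither matches the treatment schedule. The sole-agent description also carries the argument. The statement uses it to set aside the WHI combined-hormone findings and to bring in the estrogen-alone arm as the relevant comparison. If estradiol is never taken alone, that argument does not describe this trial.

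At stake is what participants are told. They are healthy volunteers with little prospect of direct benefit, and the protocol presents this text as consent wording. The sentence would misdescribe their exposure and give them a reason for low risk that does not apply to them. No endpoint, power calculation or analysis depends on it.

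**Working it through.** The statement gives one week of combined use, with estradiol otherwise alone. The check is whether the schedule reproduces that.

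Scheduled exposure by phase, from Section 5.2, Section 6 and Table 2 in Section 1.5:

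| Phase | Weeks | Estradiol | Progesterone |
|---|---|---|---|
| Hypogonadism | 0-4 | placebo | placebo |
| Addback | 4-6 | 2 mg bid | 200 mg bid |
| Withdrawal | 6-8 | placebo | placebo |

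1. Days on active estradiol: 2 weeks × 7 = 14.
2. Days on active progesterone: the same 14.
3. Combined days: 14.
4. Days on estradiol without progesterone: 14 − 14 = 0.
5. Combined days according to the statement: 7, and 7/14 = 50% of the scheduled figure.
6. Days on estradiol alone that the statement would imply over a two-week addback: 14 − 7 = 7, against 0 scheduled.

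The one-week figure is not reproduced. The dose rationale in Section 1.5 also gives both hormones for two weeks, so every account of the regimen agrees.

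The sentence could have been carried over from the earlier study, but it does not fit that study either. The text before Table 2 describes the earlier protocol as using "at least twice the doses of both E2 and P4 proposed here) and for a longer duration (8 weeks versus 2 weeks". Table 2 shows both hormones active in its two-week low-dose phase and its six-week high-dose phase: 2 + 6 = 8 weeks combined and 0 weeks of estradiol alone.

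Section 4.4.1 has two provisions that could alter an individual's exposure: dose titration for side effects, and restarting hormone replacement if severe mood symptoms occur during withdrawal. Neither specifies estradiol alone or a one-week combination, so neither explains the wording.

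**The case against.** The conflict in the text is not in dispute. The best case on the other side is that little follows from it.

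- **The low-risk conclusion survives.** The statement also contrasts brief use here with chronic use of different compounds, and closes on dose and duration. Section 1.5 separately notes that complications are unlikely "in the younger age group of women who participate in this study". This stands. Two weeks is still short, and only the sole-agent reasoning and the comparison built on it fail.
- **Combined use is not hidden.** Section 1.5 covers combined oral-contraceptive harms, has its own text on giving the three drugs together, and tabulates adverse events from the earlier combined regimen. This also stands for an IRB or DSMB member reading the protocol. It does not correct a false sentence that the protocol assigns to participants.
- **The consent form was not reviewed.** It may describe the two-week combination correctly elsewhere. The criticism therefore applies to the quoted statement, not to the consent form as a whole.
- **Removing the estrogen-alone comparison removes an adverse finding.** That sentence reports increased stroke risk. Stroke is already listed among the combined-hormone harms in the same statement, so nothing is lost. Keeping the comparison, with a clear note that it is not this regimen, would also cure the error.
- **The day counts are scheduled values.** Individual exposure can differ under Section 4.4.1. This is correct, and the counts are given here as scheduled.

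**Conclusion.** The concern holds. The statement is wrong as written in Section 1.5 and Appendix C. Scheduled combined exposure is 14 of 14 active-hormone days, twice the stated 7, and no day of estradiol alone is scheduled. Changing one week to two would not be enough, because the sole-agent claim, the inference from it and the estrogen-alone comparison would remain.

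The size of the problem is limited to risk disclosure. Nothing here shows that the actual risk is high, and dose, schedule, sample size, power and analysis are untouched. The consent impact rests on the protocol's own word that the statement was placed in the consent documents. The correction should be made because the error is certain, concerns text meant for healthy volunteers and is inexpensive to remove.

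**What to change.** In Section 1.5, Appendix C and the consent form:

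- State that estradiol (4 mg/day) and progesterone (400 mg/day) are taken together for the whole two-week addback, and that estradiol is not taken alone.
- Delete the sole-agent clause and the inference that follows from it.
- Delete the estrogen-alone comparison, or keep it with a plain note that it does not describe this regimen. Deletion is simpler.
- Rest the reassurance on the short duration, the younger age group and the difference between these compounds and those used in WHI.

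The cost is rewording in two places in the protocol document and in the consent form, plus IRB review of the corrected text. Dose, schedule, sample size and analysis do not change.
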